### Protocol deviations

Critical and major protocol deviations (automatic or manual) will be summarized in the randomized subjects.

## **4.3 PRIMARY ENDPOINT(S) ANALYSIS**

### **4.3.1 Definition of endpoint(s)**

The primary endpoints are as follows for the evaluation of immunogenicity:

- HAI Ab titers obtained on D28
- Seroconversion (titer <10 [1/dil] at D0 and post-injection titer  $\geq 40$  [1/dil] at D28, or titer  $\geq 10$  [1/dil] at D0 and a  $\geq 4$ -fold increase in titer [1/dil] at D28)

The primary endpoints will be evaluated using the result from 4 strains to be determined by MHLW contained in the QIV-SD used for the HAI testing.

#### 4.3.2 Main analytical approach

A superiority approach will be used to compare post-vaccination GMTs and seroconversion rates between QIV-HD and QIV-SD groups for each strain using a 1-sided test with Type I error rate of 0.025 following the individual hypotheses. The definitions of superiority correspond to statistical superiority where 1.0 is used as the threshold for the ratio of GMTs and 0 is used as the threshold for difference of seroconversion rates. Superiority as defined in the primary objective is based on following individual hypothesis:

$$H_0^s: \frac{GMT_{QIV-HD}^s}{GMT_{QIV-SD}^s} \leq 1 \Leftrightarrow \log_{10}(GMT_{QIV-HD}^2) - \log_{10}(GMT_{QIV-SD}^s) \leq \log_{10}(1) = 0$$

$$H_A^s: \frac{GMT_{QIV-HD}^s}{GMT_{QIV-SD}^s} > 1 \Leftrightarrow \log_{10}(GMT_{QIV-HD}^s) - \log_{10}(GMT_{QIV-SD}^s) > \log_{10}(1) = 0$$

$$H_0^s: \pi_{QIV-HD}^s - \pi_{QIV-SD}^s \leq 0$$

$$H_A^s: \pi_{QIV-HD}^s - \pi_{QIV-SD}^s > 0$$

where

- $s$ : strain
- $\pi$ : the seroconversion rate

the statistical methodology will be based on the use of the lower bound of the 2-sided 95% CIs of the ratio of post-vaccination GMTs and difference in seroconversion rates between the QIV-HD group and QIV-SD group. The 95% CIs will be calculated by normal approximation of log-transformed titers for GMTs and by the Wilson score method without continuity correction, quoted by Newcombe, for seroconversion rates (2). The superiority will be demonstrated if the lower bounds of CIs are greater than the thresholds defined as 1.0 for ratio of GMTs and 0 for differences in seroconversion rates. The graphical presentations by GMTs and seroconversion rates will also be provided with their 95% CIs.

The superiority objective will be achieved if the superiority is demonstrated for all of the 4 strains for both GMTs and seroconversion rates. For the objective, it is planned to use the HAI assay results using both the QIV-HD and QIV-SD strains as test antigens for all the subjects irrespective of the vaccine received. The FAS will be used for the immunogenicity analyses.

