6.5 RANDOMIZATION AND ALLOCATION PROCEDURES

For the randomization of dose numbers, the sponsor or designee will supply a computer generated randomization list, which will be used for the labeling and packaging.

On the day of enrollment, subjects who meet the inclusion/exclusion criteria and sign the ICF will be randomly assigned to either of the 2 study groups (QIV-HD by IM route or QIV-SD by SC route) in a 1:1 ratio by block randomization, stratified according to age (i.e., 60 to 64, 65 to 74, and 75 years of age and older), and site.

Study staff will connect to the IRT, enter the identification and security information, and confirm a minimal amount of data in response to IRT prompts. The IRT will then provide the vaccine dose number and have the site administrator confirm it. Dose numbers will be recorded on the source documents and CRBs. The full detailed procedures for group allocation are described in the IRT operation manuals. If the subject is not eligible to participate in the study, then the information will only be recorded on the screening/enrollment log.

Subject numbers that are assigned by the IRT will consist of a 12-digit string (a 3-digit country identifier, a 4-digit study center identifier, and a 5-digit subject identifier). For example, Subject 392000100005 is the fifth subject enrolled in Center Number 1 in Japan (392 being Japan country code).

Subject numbers should not be reassigned for any reason. The randomization codes will be kept securely in the IRT and an internal system.

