12.1.1.2 Statistical Methods

Immunogenicity

Assuming that log10 transformation of the data follows a normal distribution, the log10 (data) will be used for the statistical analysis, then antilog transformations will be applied to the results of calculations, in order to provide the results in terms of GMTs.

The statistical methodology will be based on the use of the 2-sided 95% CIs of the ratio of post-vaccination GMTs and difference in seroconversion rates between the QIV-HD group and QIV-SD group. The 95% CIs will be calculated by normal approximation of log-transformed titers for GMTs and by the Wilson score method without continuity correction, quoted by Newcombe, for seroconversion rates (32). The margins used for superiority hypotheses testing are 1.0 for GMTs and 0% for seroconversion rates.

The superiority objective will be achieved if the superiority is demonstrated for all of the 4 strains for both GMTs and seroconversion rates. For the objective, it is planned to use the HAI assay results using the strains contained in the QIV-SD determined by the MHLW for all subjects. The per-protocol analysis set (PPAS) and full analysis set (FAS) will be used for the immunogenicity analyses. Conclusion will be made based on the FAS results.

Sensitivity analyses will be also performed according to the following analyses for the ratios of post-vaccination GMTs and the differences in the seroconversion rates in the FAS and PPAS:

- Analysis of covariance (ANCOVA) with treatment group and age group (60 to 64, 65 to 74, and 75 years of age and older) of the stratification factor as fixed effects, and pre-vaccination value (V01) as a covariate for ratio of GMTs.
- Cochran-Mantel-Haentzel method stratified on age group (60 to 64, 65 to 74, and 75 years of age and older) of the stratification factor for difference in seroconversion rates.

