**Table 3 – Statistical Assumptions for the Sample Size Calculation**

Statistical Criteria	Assumption
Allocation ratio	1:1 between QIV-HD and QIV-SD
Overall power	>90%
Type I error	One-sided 0.025 on each strain for each endpoint
Expected GMT ratio	1.6 for all strains
Standard deviation for the log titers (in log10 scale)	0.7 for all strains
Expected seroconversion rates	40% for 2 strains with an increase of 17% in the QIV-HD group and 50% for another 2 strains with an increase of 8% in the QIV-HD group
Attrition rate	5% in the FAS

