#### 4.3.3 Sensitivity analysis

Sensitivity analyses will be also performed according to the following analyses for the ratios of post-vaccination GMTs and the differences in the seroconversion rates in the FAS:

- Analysis of covariance (ANCOVA) with treatment group and age group (60 to 64, 65 to 74, and 75 years of age and older) of the stratification factor as fixed effects, and pre-vaccination value (V01) as a covariate for ratio of GMTs.
- Cochran-Mantel-Haentzel method stratified on age group (60 to 64, 65 to 74, and 75 years of age and older) of the stratification factor for difference in seroconversion rates.

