#### **4.4.1.3 Subgroup analyses**

GMTs at V02, seroconversion rates at V02, and percentages of subjects with titers  $\geq 40$  (1/dil) and their corresponding 95% CIs will be presented on the FAS by following subgroups:

- Age group (60 to 64 years, 65 to 74 years, and  $\geq 75$  years; 60 to 64 years and  $\geq 65$  years)
- Sex (Male, Female)
- Previous influenza vaccination status (Yes, No)

- Baseline seropositivity status (Seronegative[<1:10], Seropositive[ $\geq 1:10$ ])

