##### *Confidence interval for the GMT ratio between 2 groups*

The calculations of the 95% CI for the GMT ratio between 2 groups are as following:

Logarithmic transformation of the individual titers will be calculated first. Assuming that individual  $\log_{10}$  (titer) is normally distributed, the 95% CI for the difference in  $\log_{10}$  (GMT) between group  $i$  and group  $j$  will be in the form:

$$\bar{X}_i - \bar{X}_j \pm t(1 - \alpha/2, n_i + n_j - 2) \cdot s \sqrt{1/n_i + 1/n_j},$$

where  $\bar{X}_i = \log_{10}$  (GMT) is the mean of  $\log_{10}$  (titer) of group  $i$ ,

$S^2 = [(n_i - 1)S_i^2 + (n_j - 1)S_j^2]/(n_i + n_j - 2)$  is the pooled sample variance,

$n_i$  and  $S_i^2$  are the sample size and sample variance of group  $i$ ,

$t(1 - \alpha/2, n_i + n_j - 2)$  is the  $100(1 - \alpha/2)$  percentile of the  $t$ -distribution with degrees of freedom (df) =  $n_i + n_j - 2$ .

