### ***Confidence interval of the difference in proportions***

The 2-sided 95% CI of the difference in proportions will be computed using the Wilson Score method without continuity correction, quoted by Newcombe (2) as follows:

Let  $\hat{\theta} = \pi_A - \pi_B$ , then if  $L = \hat{\theta} - \delta$  and  $U = \hat{\theta} + \varepsilon$  are respectively the lower and the upper limits of the CI, where:

$$\delta = Z_{0.025} \sqrt{\left\{ \frac{l_1(1 - l_1)}{n_1} + \frac{u_2(1 - u_2)}{n_2} \right\}}$$
$$\varepsilon = Z_{0.025} \sqrt{\left\{ \frac{l_2(1 - l_2)}{n_2} + \frac{u_1(1 - u_1)}{n_1} \right\}},$$

$l_1$  and  $u_1$  are calculated from the CI of the single proportion in group A given by:

$$\frac{\left(2n_1p_A + Z_{0.025}^2 \pm Z_{0.025} \sqrt{\left(Z_{0.025}^2 + 4n_1p_A(1-p_A)\right)}\right)}{2(n_1 + Z_{0.025}^2)},$$

$l_2$  and  $u_2$  are calculated from the CI of the single proportion in group B given by:

$$\frac{\left(2n_2p_B + Z_{0.025}^2 \pm Z_{0.025} \sqrt{\left(Z_{0.025}^2 + 4n_2p_B(1-p_B)\right)}\right)}{2(n_2 + Z_{0.025}^2)},$$

where  $Z_{0.025}$  is the upper 97.5th percentile of the standard normal distribution.

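### The primary GMT and seroconversion intervals are valid, but neither adjusts for the D0 titer or the age stratum; adjusting would be a cheap, modest gain in precision.

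*SAP*

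**What the plan says.** - **Primary method.** SAP 4.3.2 and Protocol 12.1.1.2 base superiority on two-sided 95% limits "calculated by normal approximation of log-transformed titers for GMTs and by the Wilson score method without continuity correction". SAP 5.4.7 gives the formulas: a two-group pooled-variance t interval on log10 titer, and for proportions "The 2-sided 95% CI of the difference in proportions will be computed using the Wilson Score method without continuity correction". Neither formula has a covariate or a stratum.
- **Randomization.** Protocol 6.5 has blocks "stratified according to age (i.e., 60 to 64, 65 to 74, and 75 years of age and older), and site".
- **Adjusted analyses already planned.** Protocol 12.1.1.2 and SAP 4.3.3 list them as sensitivity analyses. For GMT: "Analysis of covariance (ANCOVA) with treatment group and age group", with the V01 titer as covariate. For seroconversion: "Cochran-Mantel-Haentzel method stratified on age group (60 to 64, 65 to 74, and 75 years of age and older) of the stratification factor", with no baseline titer.
- **Baseline titer elsewhere.** It enters the definition of seroconversion (SAP 5.4.3), and baseline serostatus is a descriptive subgroup (SAP 4.4.1.3).
- **Success rule.** SAP 4.6 requires all 4 strains to succeed on both endpoints, so there are 8 comparisons.

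**The concern.** The D0 titer is collected from nearly every subject and can be expected to predict the D28 titer. It also decides which seroconversion rule applies to a subject: a D28 titer of at least 40, or a four-fold rise. Age is a randomization stratum. Leaving both out of the primary analysis gives up precision and leaves the primary estimates exposed to chance imbalance in baseline titer. Because all 8 comparisons must succeed, precision matters most where power is lowest, which is the two seroconversion comparisons planned at 50% versus 58%. For that endpoint even the planned sensitivity analysis does not adjust for D0.

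**Working it through.** **Inputs (SAP Table 3).** 1050 per arm, 5% attrition, so 1050 × 0.95 ≈ 997 evaluable per arm; one-sided 0.025; GMT ratio 1.6; SD 0.7 on log10; seroconversion 40% versus 57% for two strains and "50% for another 2 strains with an increase of 8% in the QIV-HD group" for the rest.

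**1. Reproduce the plan's power.**
- GMT: z = log10(1.6) / (0.7 × √(2/997)) = 0.2041 / 0.03135 = 6.51; power above 0.9999 per strain.
- 57% versus 40%: SE = √((0.57×0.43 + 0.40×0.60)/997), z = 7.71; power above 0.9999.
- 58% versus 50%: SE = √((0.58×0.42 + 0.25)/997) = 0.02225, z = 3.595; power = Φ(3.595 − 1.96) = 0.949.
- Overall, strains independent: 0.949² = 0.901. With correlation 0.5 between the two limiting strains: 0.911.

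The stated 90% is reproduced. Nearly all the remaining risk sits in the two 50% versus 58% comparisons.

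**2. Check validity.** Exact enumeration of the Newcombe interval at 997 per arm gives a one-sided type I error of 0.0257 at a common rate of 50% and 0.0253 at 40%. Both are close to nominal.

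**3. Seroconversion with D0 adjustment (assumed grid).** D0 log10 mean 1.0, 1.3 or 1.6; SD 0.5; D0–D28 correlation r of 0.3, 0.5 or 0.7. Simulation of 3,000 trials per scenario, with duplicate two-fold titers, values below 10 set to 5, and D28 calibrated to 50% and 58%. Age shares were 25/50/25 with no age effect. The analysis was a Mantel-Haenszel risk difference with Sato variance over 3 age × 3 D0 strata. Overall power = [Φ(0.08/(0.02225 × ratio) − 1.96)]².

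| D0 mean | r = 0.3: SE ratio, power | r = 0.5 | r = 0.7 |
|---|---|---|---|
| 1.0 | 0.996, 0.904 | 0.988, 0.909 | 0.948, 0.934 |
| 1.3 | 0.988, 0.909 | 0.994, 0.905 | 0.972, 0.920 |
| 1.6 | 0.977, 0.916 | 0.994, 0.905 | 0.991, 0.907 |

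- The median ratio is 0.988, so median overall power is 0.909. At between-strain correlation 0.5 the range is 0.913 to 0.940, median 0.918.
- The top value is a single corner, with 54% of subjects below 10 at baseline.
- Equivalent extra randomized subjects = 2 × (997/ratio² − 997)/0.95: about 17 at the low end, 50 at the median and 235 at the top.
- The mean estimate stayed within 0.0003 of the unadjusted difference. One-sided type I error was 0.023 to 0.028 (Monte Carlo SE 0.003), against 0.022 to 0.029 unadjusted.
- The smallest stratum held about 48 subjects over both arms.
- A separate set of 15 assumed scenarios, varying baseline level and how the rise depends on it, gave 0.901 to 0.936, median about 0.904.

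**4. Age alone (assumed).** Stratum rates differing by ±5, 10 or 15 points give overall power of 0.903, 0.908 or 0.918.

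**5. GMT with ANCOVA (same D0 grid, 1,500 trials per scenario).** The width ratio is 0.965 to 0.737, so the interval is about 4% to 26% narrower. The planned 1.39–1.84 becomes between 1.40–1.83 and 1.44–1.78. If 5% of subjects lack D0 and are dropped, the ratio is 0.991 to 0.757, still 1% to 24% narrower than the unadjusted interval on everyone. In closed form the width scales with √((1 − r²)/(1 − m)), where m is the share missing D0. The advantage is lost only when m exceeds r², which is 9% at r = 0.3. SAP 5.4.4.2 expects at most 5% missing immunogenicity data.

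**The case against.** The strongest reply is that nothing here is wrong. An unadjusted primary analysis with adjusted sensitivity analyses is a legitimate choice, fixed in the protocol. The planned ANCOVA will be run in any case, so for GMT the change is one of label and adds no power. For seroconversion the median gain is under one point (0.901 to 0.909). Correlation of 0.2 to 0.6 between the limiting strains already moves unadjusted power to 0.903–0.914. Changing both primary methods this late also has a cost.

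Most of this stands, and it limits the point to an optional improvement. It does not remove the point: the data are already collected, the hypotheses are unchanged, and the seroconversion sensitivity analysis still lacks D0.

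A reader might infer more than the documents support:
- **That the primary analysis is biased or the trial underpowered.** Steps 1 and 2 show otherwise.
- **That the plan ignores baseline.** Seroconversion is itself defined from D0. What is missing is D0 as a covariate.
- **That no adjustment is planned.** SAP 4.3.3 plans it, as sensitivity analysis.
- **That site should be adjusted for too.** Randomization is stratified by site and SAP 5.4.6 pools centers, but no gain from site was evaluated and none is claimed.

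**Conclusion.** The point holds as one of efficiency. The primary intervals are sound and the plan meets about 90% power on its own inputs. On assumed inputs, D0 adjustment shrinks the seroconversion standard error by about 0.4% to 5% and puts overall power at about 0.90 to 0.94, median about 0.91 under independence. The whole power gain comes through the two 50% versus 58% comparisons. For GMT the gain is a narrower interval and protection from chance baseline imbalance, not power.

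The size is uncertain. The documents give no D0 distribution, no D0–D28 correlation, no between-strain correlation and no seroconversion rates by age or baseline titer. The 0.90 to 0.94 range reflects D0 only, since no age effect was simulated. This is a change the sponsor could make, not one it must make.

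**What to change.** By a dated SAP revision before database lock and unblinding, recorded in SAP 5.2 as a change from Protocol 12.1.1.2:

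1. **GMT.** Make the ANCOVA already planned in SAP 4.3.3 (group, age stratum, log10 D0 titer) the primary analysis.
2. **Seroconversion.** Make primary a Mantel-Haenszel risk difference with Sato variance, stratified by the 3 age groups and 3 D0 categories (<10, 10 to <40, ≥40; SAP 4.4.1.2 already reports these cut-points). Superiority still requires a lower 95% limit above 0.
3. **Sensitivity.** Keep both current unadjusted intervals on the full FAS. Report how many FAS subjects leave the ANCOVA for lack of a D0 titer. The no-replacement rule stays; if the sponsor prefers to retain these subjects by filling in the covariate, state that as an explicit exception.
4. **Minimum alternative.** If the primary method is not changed, add D0 titer category to the CMH in SAP 4.3.3.

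**Cost.** No new data or subjects; the ANCOVA is already planned and the 9-stratum difference needs some programming. The change to a protocol-specified method is late: first randomization was 21-Oct-2020, SAP 1.0 is dated 08-Jan-2021, and the planned last visit is 19-Jan-2021. It carries over to the PPAS analysis in SAP 4.3.4. Subjects whose D0 draw fails are still vaccinated (Protocol 5.1.4) and can enter the FAS, so they would leave the primary GMT analysis; they already cannot contribute to seroconversion. The minimum alternative leaves the primary analysis untouched.

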#### 4.3.3 Sensitivity analysis

Sensitivity analyses will be also performed according to the following analyses for the ratios of post-vaccination GMTs and the differences in the seroconversion rates in the FAS:

- Analysis of covariance (ANCOVA) with treatment group and age group (60 to 64, 65 to 74, and 75 years of age and older) of the stratification factor as fixed effects, and pre-vaccination value (V01) as a covariate for ratio of GMTs.
- Cochran-Mantel-Haentzel method stratified on age group (60 to 64, 65 to 74, and 75 years of age and older) of the stratification factor for difference in seroconversion rates.

#### **4.3.4 Supplementary analyses**

The GMTs and seroconversion rates will be analyzed using similar main analytical approach as described in [Section 4.3.2](#) on the PPAS to compared the endpoints between the QIV-HD and QIV-SD groups.

#### **4.3.5 Subgroup analyses**

Subgroup analyses will be performed on the primary endpoint on the FAS across the following subgroups:

- Age group (60 to 64 years, 65 to 74 years, and  $\geq 75$  years; 60 to 64 years and  $\geq 65$  years)

The ratios of post-vaccination GMTs between the QIV-HD and QIV-SD groups and the differences in seroconversion rates with the corresponding 95% CIs will be presented. No statistical testing will be conducted for the subgroup analyses.

### **4.4 SECONDARY ENDPOINT(S) ANALYSIS**

#### **4.4.1 Key/Confirmatory secondary endpoint(s)**

##### **4.4.1.1 *Definition of endpoint(s)***

The secondary endpoints for the evaluation of immunogenicity are:

- HAI Ab titers obtained on D0 and D28
- Individual HAI titers ratio D28/D0
- Seroconversion (titer  $< 10$  [1:dil] at D0 and post-injection titer  $\geq 40$  [1:dil] at D28, or titer  $\geq 10$  [1:dil] at D0 and a  $\geq 4$ -fold increase in titer [1:dil] at D28)
- Percentage of subjects with titers  $\geq 40$  (1:dil) at D0 and D28

The statistical analyses for secondary endpoints will be performed on the FAS using all 6 strains tested.

##### **4.4.1.2 *Main analytical approach***

For descriptive purposes, following statistics with their corresponding 95% CI will be displayed:

- HAI GMTs and the ratios of the GMTs between the QIV-HD and QIV-SD groups at V02

- GMs of HAI titers
  - Pre-dose (V01) and post-dose (V02)
  - Post-dose response based on pre-dose (individual titer ratio V02/V01)
- Seroconversion rates and the difference between the QIV-HD and QIV-SD at V02
- Number and percentage of subjects with HAI titers  $\geq 40$  (1/dil) at each time point
- Distribution of HAI titers at each time point

Graphical presentations will be provided with their 95% CIs by:

- HAI GMTs at V02
- GMs of individual titer ratio V02/V01
- Seroconversion rates at V02

Reverse cumulative distribution curves (RCDCs) against each strain will be performed for pre-dose (V01) and post-dose immunogenicity (V02).

As a summary of hemagglutinin (HA) antibody response antigen, the following parameters will be displayed:

- Pre-dose (V01) and Post-dose (V02)
  - Geometric mean
  - Number and percentage of subjects with HAI titer  $\geq 1:10$
  - Number and percentage of subjects with HAI titer  $< 1:10$
  - Number and percentage of subjects with HAI titer  $\geq 1:40$
- Post-dose response based on pre-dose
  - Geometric mean (of individual ratio)
  - Seroconversion rate

More detailed summaries of the HA antibody response will also be provided by strain, adding median, Q1, Q3, minimum, maximum, mean and SD of Log10 transformed value for continuous data of titers.

#### **4.4.1.3 Subgroup analyses**

GMTs at V02, seroconversion rates at V02, and percentages of subjects with titers  $\geq 40$  (1/dil) and their corresponding 95% CIs will be presented on the FAS by following subgroups:

- Age group (60 to 64 years, 65 to 74 years, and  $\geq 75$  years; 60 to 64 years and  $\geq 65$  years)
- Sex (Male, Female)
- Previous influenza vaccination status (Yes, No)

- Baseline seropositivity status (Seronegative[<1:10], Seropositive[ $\geq 1:10$ ])

#### **4.4.2 Supportive secondary endpoint(s)**

Not applicable

### **4.5 TERTIARY/EXPLORATORY ENDPOINT(S) ANALYSIS**

#### **4.5.1 Definition of endpoint(s)**

Not applicable

#### **4.5.2 Main analytical approach**

Not applicable

### **4.6 MULTIPLICITY ISSUES**

It is required to demonstrate superiority on the FAS in all 4 strains determined by the MHLW to be contained in the QIV-SD for both GMTs and seroconversion rates. Therefore, no multiplicity issues are to be considered.

### **4.7 SAFETY ANALYSES**

All safety analyses will be performed on the SafAS as defined in [Section 3](#), unless otherwise specified, using the following common rules:

- The analysis of the safety variables will be essentially descriptive, and no testing is planned. However, the 95% CI (Clopper-Pearson method) will be provided.
- Safety data in subjects who do not belong to the SafAS will be provided (in the listings of Appendix).

#### **4.7.1 Extent of exposure**

Not applicable

